5.4. Prior and Concomitant Medications and Excluded Therapies

At each study visit, the study center will capture any and all medications taken by the subject since the last visit or during the visit (as applicable). Concomitant medications include prescription medications, non-prescription medications, therapies, and dietary supplements. The use of all inhaled and/or IV antibiotics for respiratory exacerbations during the 12 months prior to Screening will be recorded.

The following medications are excluded from use during the study:

- Systemic immunosuppressive drugs including
- An oral corticosteroid burst of > 7 days duration
- Any investigational drug therapy
- Prophylactic and chronic doxycycline

Effective current therapies should not be discontinued for the sole purpose of participating in this study. Subjects may receive medications as supportive care or to treat AEs as deemed necessary by the investigator or the subject's physician. Should subjects have a need to initiate treatment with any excluded concomitant medication, the Medical Monitor must be consulted prior to initiation of the new medication. In instances where an excluded medication is initiated prior to discussion with the Sponsor, the investigator must notify Gilead Sciences as soon as he/she is aware of the use of the excluded medication. The allowed concomitant medication(s) for CF must be maintained at a stable dose throughout the duration of the study.

5.5. Concomitant Medication Management

Subjects must remain on stable CF medication regimens from 30 days prior to Baseline, and it is recommended they remain on those medications through the Follow-up visit. If a change in CF medication regimen is required during the course of the study, please contact the medical monitor prior to initiation of therapy.

Specific requirements apply to inhaled CF medications:

- At the time of study entry, subjects who are on a stable regimen of inhaled antibiotics that are continuously administered should remain on those antibiotics throughout the study.
 - A stable regimen of continuous or continuous alternating antibiotics is at least 2 “on-treatment” cycles (about 2 months) prior to Baseline.
- At the time of study entry, subjects who are on a stable regimen of inhaled cycling antibiotics (e.g. aztreonam for inhalation [Cayston], inhaled tobramycin [TOBI and TIP], inhaled colistin) should remain on these antibiotics throughout the study. Inhaled cycling antibiotics should be administered in 28-day-on/28-day-off cycles.
 - A stable regimen of cycling antibiotics is at least 2 “on/off” cycles (about 4 months) prior to Baseline.
- Standard of care inhaled CF therapies (eg, bronchodilators, dornase alpha, inhaled antibiotics, hypertonic saline, inhaled mannitol, inhaled corticosteroids) will be withheld prior to study specified spirometry according to Section [6.3.6](#)

5.6. Accountability for Study drug

The investigator is responsible for ensuring adequate accountability of all used and unused study drug. This includes acknowledgement of receipt of each shipment of study drug (quantity and condition).

Study drug accountability records will be provided to each study site to:

- Record the date received and quantity of study drug
- Record the date, subject number, the study drug kit number dispensed
- Record the date, quantity of used and unused study drug.

For additional information about study drug accountability and return, refer to Section [9.1.7](#).

5.7. Rescreening of Study Subjects

Subjects may be rescreened only once if they meet no more than 1 of the criteria below. A request for rescreening form must be completed and approved by the medical monitor prior to a subject rescreen.

If a subject is randomized but not dosed due to a safety concern after the FRI has occurred, the subject may be rescreened with Medical Monitor approval, and may opt to not participate in the FRI sub-study at that site.

- 1) A subject is unable to produce adequate sputum during the first attempt during screening for any required inclusion/exclusion criteria related to sputum bacteriology.
- 2) A subject that requires a new course of oral or IV antibiotics, systemic corticosteroids or is hospitalized during screening, may rescreen 30 days after hospital discharge or at least 30 days after the last course of antibiotics/corticosteroids
- 3) Any acute “non-CF related” illness within 2 weeks prior to Baseline (eg, gastroenteritis).
- 4) An investigator may petition the medical monitor for a rescreen of subject for a single criterion that is not mentioned above providing details and rationale for the rescreen and completing a request for rescreening form.

6. STUDY PROCEDURES

The study procedures to be conducted for each subject enrolled in the study are presented in tabular form in [Table 6-1](#) and described in the text that follows. Additional information is provided in the study procedures manual.

The investigator must document any deviation from protocol procedures and notify the sponsor or contract research organization (CRO).

6.1. Details of Study Visits

6.1.1. Subject Enrollment and Treatment Assignment

It is the responsibility of the Investigator to ensure that subjects are eligible to participate in the study prior to randomization or enrollment and throughout the study.

Once consent has been obtained, all screening tests and procedures have been assessed, and study eligibility has been confirmed, eligible subjects will be randomized to study treatment as described in [Section 3.3](#).

The study center will not be released to initiate dosing until:

- The Institutional Review Board (IRB) or Ethics Committee (EC) reviewed and approved the study and the informed consent document;
- All required regulatory documents have been submitted to and approved by Gilead or the CRO;
- A master services agreement and/or study agreement is executed;
- The site initiation meeting has been conducted by the Gilead clinical monitor (or designee). The initiation meeting will include a review of the protocol, the IB, and investigator responsibilities.

Table 6-1. Schedule of Assessments

[figure not shown]
Week	Screening	Baseline Randomization	Optional PK	Study Drug Administration Visits						Optional PK	Study Drug Administration Visit	Primary Endpoint	Optional Open-Label Extension						30-Day Follow-Up Visit	Early Termination Visit	
				1	2	3	4	5	6				7	8	9	10	11, 13-15, 17-19, 21-23	12			16
Day	-30 to -1	1 ¹	5	8	15	22	29	36	43	48	50	57	64	71		85	113	141	169		
Window in days			±1	±3	±3	±3	±3	±3	±3	±1	±3	-3 to +4	±3	±3	±3	±3	±3	±3	±3	±7	
Home Health Visit Option						X		X		X	X				X						
Withhold all inhaled CF therapies morning of study visit	X ⁹	X		X			X		X			X		X			X		X	X	
Written Informed Consent	X																				
CFQ-R ^a		X			X		X		X			X				X	X	X	X	X	X
TSQM (if available) ^a		X					X					X				X	X	X	X		
SNOT-22 (if available) ^a		X										X							X		
Medical History	X																				
Concomitant Medications	X	X	X	X	X	X	X	X	X	X		X	X	X		X	X	X	X	X	X
Pulmonary Exacerbation Evaluation		X		X	X		X		X			X	X	X		X	X	X	X	X	
Complete Physical Exam ^b	X																			X	X
Symptom Driven Physical Exam ^b		X					X					X				X	X	X	X		
Vital Signs	X	X		X	X	X	X	X	X		X	X	X	X		X	X	X	X	X	X
Blood for Safety Labs ^c	X	X			X		X					X					X			X	X
ESR ^f	X											X								X	
Urine Cotinine	X						X					X					X				
Urinalysis	X	X			X							X					X			X	X
Serum Pregnancy Test ^d	X																			X	X
Urine Pregnancy Test		X			X		X		X			X	X	X		X	X	X	X		
Oxygen Saturation		X										X								X	X
Screening Spirometry	X ^m																				

Week	Screening	Baseline Randomization	Optional PK	Study Drug Administration Visits						Optional PK	Study Drug Administration Visit	Primary Endpoint	Optional Open-Label Extension						30-Day Follow-Up Visit	Early Termination Visit	
				1	2	3	4	5	6				7	8	9	10	11, 13-15, 17-19, 21-23	12			16
Day	-30 to -1	1 ¹	5	8	15	22	29	36	43	48	50	57	64	71	85	113	141	169			
Window in days			±1	±3	±3	±3	±3	±3	±3	±1	±3	-3 to +4	±3	±3	±3	±3	±3	±3	±3	±7	
Home Health Visit Option						X		X		X	X				X						
Pre- and post-bronchodilator Spirometry ^e		X			X		X		X			X		X			X		X	X	X
PEFR	X	X ^p		X		X		X			X				X		X				
Chest X-ray ^f	X																				
ECG	X	X					X				X					X		X	X		
Induced sputum for biomarkers		X					X				X				X			X	X	X	
Spontaneous sputum for microbiology ^g	X, X				X				X								X				
FRI Scan ^h		X									X										
Blood for PK ⁱ		X		X	X		X		X		X									X	
PK sub-study			X						X												
Anti-drug Antibodies		X					X				X					X		X	X	X	
Blood for Biomarkers	X	X			X		X				X								X	X	
Blood for RNA Biomarkers		X					X				X								X	X	
Blood for CF genotyping ^l		X																			
Optional blood sample for genomic research ^l		X																			
Randomization		X																			
Study drug administration ^k		X		X	X	X	X	X	X		X	X ⁿ	X-weekly through week 23-X								
Adverse Events	X	X	X	X	X	X	X	X	X	X	X	X	X ^o	X ^o	X ^o	X ^o	X ^o	X	X	X	
Musculoskeletal Symptom Assessment	X	X					X				X				X	X	X	X	X		

a Questionnaires should be obtained prior to any other procedures. At visits where there are multiple questionnaires, the CFQR should be completed first, then SNOT-22 and then TSQM. If on a given visit SNOT-22 is not done then the CFQ-R is completed first and then the TSQM.

- b Includes height at screening visit and weight at all visits and to be conducted prior to dosing. A complete physical examination will be performed at screening and the 30-day Follow-up Visit. A symptom-driven physical examination will be performed at the Baseline, Week 4, 8, 12, 16, 20 and 24, and can be performed as needed at other study visits.
- c Safety labs include CBC with differential, chemistry panel.
- d For female subject post-menopausal for less than 2 years, if FSH < 40 mIU/ mL a serum pregnancy test will be required.
- e Subjects will withhold their standard of care inhaled CF therapies prior to study specific spirometry
- f Chest x-ray will be obtained during the screening period if subject does not have a CT scan, MRI or chest x-ray obtained in the 90 days prior to Baseline.
- g Spontaneous and induced sputum should be obtained AFTER spirometry and FRI (if applicable) have been completed. If spontaneous sputum cannot be obtained, a throat swab may be used for microbiology culture. A second spontaneous sputum microbiology for culture will be collected in the screening period.
- h For subjects enrolled in the FRI sub-study only. Subjects will withhold their standard of care inhaled CF therapies prior to FRI.
- i At Baseline, PK should be obtained prior to and 2 hours after study drug administration. At all other visits with study drug dosing, PK should be performed prior to study drug administration. Subjects who consent to the optional PK sub-study will have one additional single PK sample collected at Day 5 (± 1) and Day 48 (± 1). Optional Day 5 PK and Day 8 should occur at least 1 day apart.
- j Blood for CF genotyping should be taken at baseline for subjects who do not have a historical genotype on file, but may be collected at any time during the study, if necessary. Blood for optional genomic research should only be taken from subjects who consented to this optional procedure. It should be taken at baseline, but may be collected at any time during the study, if necessary.
- k Observe subject for 2 hours after study drug administration on Day 1, and for 30 minutes after study drug administration at all other visits during the blinded phase of the study.
- l The baseline/randomization visit may be split over 2 days as needed. If the visit is split over 2 days, the following procedures should be done on the first day prior to standard of care inhaled CF therapies as indicated in Section 5.5: questionnaires, urine pregnancy test (for women of childbearing potential only), oxygen saturation, pre- and post-bronchodilator spirometry, and FRI. Subjects must withhold their standard of care inhaled CF therapies again the next morning and perform spirometry prior to any remaining study procedures and study dosing. The day on which the first dose of study drug is administered is Baseline.
- m Two spirometry measures (pre-bronchodilator) taken at least 4 days apart (one during Screening, one at Baseline) must be taken to meet inclusion criterion 7.
- n Study drug dosing will occur at Week 8 only for subjects who elect to enroll in the open-label extension and only after all other procedures have been completed.
- o Subjects enrolled into the open-label extension may request assistance administering the SC injections either by returning to the clinic or utilizing a home health care service provided by the Sponsor to ensure proper dosing and adherence. If determined acceptable by the DMC, home self-administration may be conducted in the OLE.
- p PEFR will be performed at Baseline only if baseline procedures are conducted over 2 days and induced sputum was conducted on Day -1 to confirm subjects are stable enough to be dosed.
- q As screening will occur over at least two different days, subjects should only be asked to withhold these medications the morning of their screening spirometry assessment and only after they have been properly consented.
- r To be conducted at the site's local lab.

Figure 6-1. Suggested Schedule for Key Screening and Baseline Procedures

6.1.2. Screening Period (Day -30 to -1)

Subjects will be screened up to 30 days prior to randomization/enrollment to determine eligibility for participation in the study. Written informed consent must be obtained from each subject before initiation of any Screening procedures. After informed consent is obtained, screening procedures outlined in Table 6-1 and described in the following text will be initiated.

The screening procedures may require multiple visits. Medical history taken during Screening will also include a 1-year history of hospitalizations and IV, inhaled, and oral antibiotic therapy for pulmonary exacerbations.

Two pre-bronchodilator screening spirometry measures taken at least 4 days apart (one during Screening, one at Baseline) must be taken to meet Inclusion Criterion 7 (see Section 6.3.6).

Subjects meeting all of the inclusion criteria and none of the exclusion criteria are eligible for Randomization (Baseline). Subjects who do not meet the eligibility criteria will be excluded from randomization and may be considered for rescreening for the study in consultation with the medical monitor.

From the time of obtaining informed consent through the first administration of study drug, record all SAEs, as well as any AEs related to protocol-mandated procedures on the AE case report form (CRF/eCRF). All other untoward medical occurrences observed during the screening period, including exacerbation or changes in medical history are to be captured on the medical history CRF/eCRF. See Section 7 Adverse Events and Toxicity Management for additional details.

6.1.3. Baseline/Randomization (Day 1)

All Baseline tests and procedures must be completed prior to randomization and dosing on Day 1 as indicated in Table 6-1.

If subjects are unable to complete all Baseline assessments in a single day, the baseline/randomization visit may be split over 2 consecutive days as needed. If the visit is to be split over 2 days, the following procedures may be done on the first day and should be done prior to standard of care inhaled CF therapies as indicated in Section 5.5:

- Refer to Figure 6-1 for recommended visit schedule and order of procedures for Screening and Baseline visits.
- Sputum induction and blood draws for safety and pre-dose PK can be performed on either day of the baseline/randomization visit, but must be performed prior to study drug dosing.
- At the Baseline/Randomization visit, subjects who meet the eligibility criteria will be randomized into the study. Study drug should be administered after randomization. Subjects will be observed for 2 hours after the last injection. Blood for PK will also be obtained 2 hours after the last injection of study drug. Day 1 will be the day on which the subject receives the first dose of study drug.

6.1.4. Blinded Treatment Period: Day 5 through Week 7

At visits in the blinded treatment period, subjects should complete the CFQ-R, SNOT-22, and the TSQM prior to all other procedures when indicated in Table 6-1. At visits where study drug dosing is indicated, the subject should be observed for 30 minutes after the last injection. Subjects who provide separate consent for the PK sub-study will provide a Day 5 plasma PK sample. At the Day 48 visit blood for PK will be obtained.

For sites and subjects utilizing home health services for at home dosing of study drug, site staff should instruct the subject on the packaging, storage, self-administration, and safe needle disposal for GS-5745. Following 2 successful doses in clinic within the blinded period, the subjects and the site may choose to utilize the home health service (See Section 6.1.6 for further information). If the home health option is utilized, subjects will be dispensed GS-5745 at the visit prior to the scheduled home health visit for Weeks 3, 5, and 7 within the blinded period.

Subjects will perform peak expiratory flow rate measurements prior to study drug administration on days when study spirometry is not performed. Doses should be administered at 1 week intervals (± 3 days), all injections for a single dose should be delivered within 1 hour, and the date/time of administration will be recorded. Please refer to the Pharmacy Manual for additional information.

6.1.5. Week 8 (-3 to + 4): Primary Endpoint and Open-Label Extension

All Week 8 tests and procedures must be completed prior to participating in the OLE and dosing as indicated in [Table 6-1](#).

Subjects who agree to participate in the OLE portion of the study will be entered into the IXRS to confirm enrollment into the open-label extension after all other procedures as indicated in [Table 6-1](#). The first dose of open-label GS-5745 should be dispensed as directed by IXRS and administered to the subject at Week 8. Sites should train the subject on administration of the study drug at this visit. Subjects will be observed for 30 minutes after the last injection for the first 2 doses.

If the home health option is utilized during OLE, subjects will be dispensed GS-5745 at the visit prior to the scheduled home health visit for Weeks 11, 13 to 15, 17 to 19 and 21 to 23.

Subjects who do not agree to participate in the OLE portion of the study will be discontinued from the study and will be asked to return to the clinic in 30 days for their 30-day Follow-up visit as indicated in [Table 6-1](#).

6.1.6. Utilization of Home Health Services

Weekly clinic visits during the study may pose a significant burden to study subjects. This burden must be balanced against the need to closely monitor these potentially vulnerable subjects during the early doses of study drug. Therefore, sites and subjects will have the option of utilizing a home health nursing organization provided by the Sponsor to complete visit procedures and study drug dosing during selected visits during the blinded and OLE portions of this study. Should the subject and site choose to utilize the home health service, blinded study visits at Weeks 3, 5, 7 and OLE visits at Weeks 11, 13 to 15, 17 to 19 and 21 to 23 may occur at the subject's home. The DMC and Gilead will be closely monitoring SC injection safety throughout the study. If it is judged in the OLE phase of the study that home self-administration without a home health provider present does not pose an unacceptable safety risk, then subjects may be trained for SC self-injection. Once the subject has successfully completed the self-administration training and is judged as capable of home SC self-administration of study drug by the trainer, the subject may begin self-administration of study drug at home without supervision at any of the remaining OLE visits mentioned above.

6.1.7. Open-Label Extension: Week 9 through 24

All OLE tests and procedures should be completed as indicated in [Table 6-1](#) for subjects participating in the OLE only.

At Week 9 and 10 site staff should instruct the subject on the packaging, storage, self-administration, and safe needle disposal for GS-5745. Following 2 successful doses in clinic within the OLE, subjects will be dispensed GS-5745 to administer Weeks 11, 13 to 15, 17 to 19, and 21 to 23 doses at home by a qualified home health service selected by the Sponsor to ensure proper dosing and adherence. In the OLE subjects will perform peak expiratory flow rate measurements prior to study drug administration on days when study spirometry is not performed. Doses should be administered at one week intervals (± 3 days), all injections for a single dose should be delivered within 1 hour, and the date/time of administration will be recorded. Please refer to the Pharmacy Manual for additional information.

6.1.8. 30-Day Follow-Up Visit

Thirty days after the last dose of study drug, subjects will return to the clinic for a follow-up visit. Procedures should be completed as indicated in [Table 6-1](#).

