1.4. Risk/Benefit Assessment for the Study

GS-5745 is currently being evaluated in 5 ongoing clinical studies for the treatment of solid tumors, UC, Crohn's Disease, RA, and COPD. From the adverse events reported in these trials none have been identified as adverse drug reactions causally related to the drug. Also, no drug interactions or contraindications have been reported.

Potential risks may include local injection site reactions and the rare possibility of hypersensitivity or allergic reactions which have been reported with the use of biologics. A single hypersensitivity reaction was observed after a second infusion in a UC subject. The subject was evaluated at the local emergency room and was discharged home in satisfactory condition. Despite this single hypersensitivity reaction after an IV infusion of GS-5745, it should be noted that GS-5745 is not considered to be a 'high risk' agonist as it acts by antagonism and targets MMP9. However, to mitigate the potential risk associated with SC administration of GS-5745, subjects will be monitored for 120 minutes after first SC injection and for 30 minutes after all subsequent SC injections of each dose during the blinded phases of Part 1 and Part 2 of the study. To be prepared for a theoretical risk of a systemic injection site reaction, study sites will be required to have on site and readily available, injectable epinephrine. Home health provider's administering the at home injections will also have readily available an auto-injectable form of epinephrine. Prior to administering drug, clinic staff and the home health provider will review the clinical manifestations of anaphylaxis and the proper use of the auto-injectable epinephrine. Unless there is an adverse event safety signal of concern observed with SC injections in the blinded phases of Part 1 and Part 2, within OLE study subjects will be monitored for 120 minutes after the first SC injection and for 30 minutes after the second SC injection. For subsequent SC injections in the OLE, subjects will be monitored for at least 15 minutes after each injection.

Only patients who are on stable CF medication regimens from 30 days prior to Baseline and throughout the duration of the study will be eligible to enroll therefore the impact on the patients' habitual standard of care should be negligible.

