OLE subjects will be instructed by clinic staff how to self-administer the SC injections using the thigh and stomach areas only. After successful training and sign-off by the study clinic and/or home health provider (where available) that the subject can correctly self-administered study drug, subjects will self-administer doses at home weekly (± 3 days) between study visits and record the doses when they are administered. Subjects who find it difficult to self-administer the study drug SC injections at home may receive assistance with the administration from the home health care service (where available) to ensure proper dosing and adherence or receive their SC injections at their local study sites. All injections should be delivered within 1 hour.

Subjects will also be instructed in the safe storage and transport of the study drugs as well as safe disposal of used syringes.

Similar to the blinded phase of the study, in OLE if the subject has a body temperature of $> 38^{\circ}\text{C}$ (100.4°F), PEF decreases by $> 30\%$ from the mean obtained during Screening during non-spirometry visits, or in the medical opinion of the investigator or home health provider the subject is unfit to receive study drug at a given visit, the subject should not be administered study drug. In consultation with the medical monitor, the Investigator may delay dosing until the parameters above are met.

If a subject fails to come to their respective study site for a scheduled study visit that includes SC administration of study drug, the investigator should contact the Gilead medical monitor to discuss if a late dose is acceptable or if the dose should be skipped.

If a subject misses 2 doses defined as the series of study drug SC injections associated with 2 study visits (clinic or home visits), the Gilead medical monitor should be contacted to discuss if the study drug should be withdrawn for that subject.

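### Section 1.4 promises at least 15 minutes of monitoring after each later open-label injection, but the conditional option to self-inject unsupervised at home has no stated substitute for it or for the provider's epinephrine

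*Protocol*

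**What the plan says.** **Monitoring.** For the OLE, Section 1.4 sets 120 minutes after the first injection and 30 after the second, unless the blinded phases raise a safety signal. It then says: "For subsequent SC injections in the OLE, subjects will be monitored for at least 15 minutes after each injection". Self-injected doses are not excepted.

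**Epinephrine.** Section 1.4 requires sites to hold injectable epinephrine. For home dosing it says that providers "administering the at home injections will also have readily available an auto-injectable form of epinephrine". The only other mention in the protocol is exclusion criterion 7, on past anaphylaxis.

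**Reaction training.** Before drug is given, Section 1.4 says, "clinic staff and the home health provider will review the clinical manifestations of anaphylaxis and the proper use of the auto-injectable epinephrine". It does not say whether the subject takes part.

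**Self-injection.** Sections 5.3 and 6.1.6 and footnote o of Table 6-1 make unsupervised home dosing conditional on DMC review, with sponsor agreement under 5.3. Each subject must then be trained and approved. Section 5.3 puts the sign-off this way: "After successful training and sign-off by the study clinic and/or home health provider (where available) that the subject can correctly self-administered study drug". After that, under 6.1.6, "the subject may begin self-administration of study drug at home without supervision at any of the remaining OLE visits mentioned above". The visits meant are Weeks 11, 13 to 15, 17 to 19 and 21 to 23.

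**Listed training.** For Weeks 9 and 10, Section 6.1.7 says that "site staff should instruct the subject on the packaging, storage, self-administration, and safe needle disposal for GS-5745". Section 5.3 limits self-injection to the thigh and abdomen, and adds: "Subjects will also be instructed in the safe storage and transport of the study drugs as well as safe disposal of used syringes".

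**The concern.** The sponsor chose two safeguards against a hypersensitivity reaction, observation and ready epinephrine, and extended both to the home through the provider. When the provider is absent, both go with the provider. The protocol then leaves open who watches the subject, for how long, and what treatment is at hand. A site following 6.1.6 to the letter would breach 1.4, and a site following 1.4 to the letter could not offer what 6.1.6 permits. The protocol is what the ethics committees approve and what the DMC works from, so a safeguard described there should match the dosing that it allows.

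**Working it through.** **Inputs.** OLE dosing lasts 16 weeks, weekly (Section 3.4). The first OLE dose is at Week 8 (6.1.5) and the last at Week 23 (Table 6-1). The home weeks are listed in 6.1.6. A syringe holds 150 mg (5.2.1). The OLE dose is 600 mg in Part 1 and 300 mg in Part 2 (3.3.3).

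**Dose count.** 23 − 8 + 1 = 16, which reproduces the protocol's 16 weekly doses. Home-eligible doses: 1 + 3 + 3 + 3 = 10. The other six are Weeks 8, 9, 10, 12, 16 and 20, and 10 + 6 = 16.

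**Ceiling per subject.** 10/16 = 62.5%, if self-injection starts at Week 11. A later start gives fewer:

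- Week 13: 9/16 = 56.25%
- Week 17: 6/16 = 37.5%
- Week 21: 3/16 = 18.75%

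In syringes, Part 1 uses 600/150 = 4 per dose, so at most 40 of 64. Part 2 uses 300/150 = 2 per dose, so at most 20 of 32.

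**Prior exposure at the earliest self-injected dose.** For a former placebo subject, Week 11 is the 4th active dose (Weeks 8, 9, 10, 11). For an active-arm subject it is the 12th (8 blinded + 4).

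**Safeguards by setting for later OLE doses.**

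| Safeguard | At the site | Home, with provider | Home, self-injected |
|---|---|---|---|
| Someone to monitor for 15 minutes | Staff present | Provider present | Not stated |
| Epinephrine | Required on site | Held by provider | Not stated |
| Anaphylaxis signs and auto-injector use | Reviewed by clinic staff | Reviewed by provider | Unclear whether the subject is included |
| Temperature and peak-flow holds (5.3) | Apply | Apply | Apply, but act only before the dose |
| Hold on clinical opinion (5.3) | Investigator | Provider | Neither is present |

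The first two entries in the last column are the gap.

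**Likelihood.** Section 1.4 reports: "A single hypersensitivity reaction was observed after a second infusion in a UC subject". Section 1.3.1 gives 221 subjects dosed. Taking these as numerator and denominator (an assumption), 1/221 = 0.45%, exact 95% CI 0.01% to 2.5%. This is a per-subject figure for any dose, mostly IV and in other diseases. It is a rough guide only, and does not measure risk at a 4th or later subcutaneous dose.

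**The case against.** The strongest reply is that unsupervised dosing is not open by default. The DMC and sponsor must first review safety data and conclude that the provider can safely be absent, and each subject must then be trained and judged capable. That question arguably takes in the loss of the provider's monitoring and epinephrine. Other protections exist: past anaphylaxis needing epinephrine is an exclusion, home dosing with a provider requires no major adverse event from earlier injections (3.3.3.1), and at least three OLE doses are given in clinic first. The one reported reaction followed a second infusion, a position that would fall within the supervised doses here, and that subject went home in satisfactory condition.

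Much of this stands as a limit on likelihood. It does not reconcile the sections. The approval step decides whether the provider may be absent, but names no replacement for what the provider supplies, and 1.4 is not made subject to it.

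A reader might go further and infer that self-injecting subjects get no reaction training. The documents do not support that. The review in 1.4 can be read as done with the subject, in which case every subject has had it at clinic doses. The Pharmacy Manual and the study procedures manual, to which the protocol refers, may also add instructions and are not available here. A reader might also expect hundreds of unsupervised doses. The ceilings are 60 × 10 = 600 in Part 1 and 90 × 10 = 900 in Part 2, or 510 and 765 after the planned 15% attrition (51 × 10 and 76.5 × 10). All of these assume that every remaining subject enters the OLE and self-injects from Week 11. Sections 5.3 and 6.1.6 point the other way: approval comes during the OLE, applies to the visits still left, and follows a period of clinic or provider dosing.

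**Conclusion.** The inconsistency is real and specific. At a self-injected dose, Section 1.4 cannot be followed alongside 5.3 and 6.1.6, and the protocol states no substitute for the provider's monitoring or epinephrine. It affects at most 10 of 16 OLE doses per subject, and fewer with a later start. Likelihood is low and severity modest.

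The conclusion rests on the protocol text alone and assumes that no unseen manual settles the point. It concerns the plan as written. A reader might infer that subjects were actually exposed to this gap, but the documents do not show it. SAP Sections 1.2 and 2.1 report that 6 subjects enrolled, short of the 10 needed for the first DMC review, and that no DMC interim analysis was performed. Nor do the documents establish that every self-injecting subject must carry an auto-injector or have another adult present. The first is a judgement for the approval step, and the second has no basis in the text.

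**What to change.** 1. Amend Sections 1.4, 5.3, 6.1.6 and 6.1.7 so that a self-injected dose requires self-observation for at least 15 minutes after the last injection of the dose, with a written instruction on when to call emergency services and when to call the site.
2. Make the self-injection sign-off explicitly cover recognising and responding to anaphylaxis.
3. Have the DMC and sponsor approval step state whether self-injecting subjects must hold an epinephrine auto-injector. If one is required and not available, the home health provider or the site gives the dose, a route that 5.3 already offers.
4. Reconcile 6.1.5, which gives 30 minutes of observation for each of the first two OLE doses, with the 120 then 30 minutes in 1.4.

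**Cost.** Wording in five sections, slightly longer training, and possibly one auto-injector per self-injecting subject: at most 60 in Part 1 and 90 in Part 2, so 150 in all. The self-injection option remains, except where a required auto-injector cannot be supplied. The efficacy analysis, sample size and blinding are untouched.
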